Participants will be asked to complete an electronic REDCap data collection questionnaire or be assisted in this by the research team by telephone if support required. Information collated will include:

- Confirmation of any change in medical and drug history, COVID-19 infection and vaccination history. If the patient answers no to all of these no further action will be taken. If they answer yes they will be asked whether it is a change in their immunosuppressive/chemotherapy/radiotherapy treatment. This will alert the Central and Local Study Teams to check the individual's medical records to confirm this change and if required the patient will be contacted to confirm. If an individual has tested positive for COVID-19 they will be asked to complete a REDCap survey about their illness and where they were treated (see section on testing positive for COVID-19 17.3.1)
- Remote cohort will receive a DBS kit and in-person cohort will provide the same blood, saliva and
 nasal samples as per baseline. For the remote cohort, participants will be asked to logon to
 REDCap to confirm they have sent a sample back to enable sample tracking and their anticipated
 vaccination date (if known). Or participants can email or telephone the study team with this
 information.

Visit 3: All participants will provide a sample **4-10 weeks post vaccination**.

Participants will be asked to complete the same electronic REDCap questionnaire as per visit 2.

Participants will be asked to provide the same samples as per visit 2 depending on whether they are the remote or in-person group.

If a participant does not to receive a booster vaccine (either because they chose not to or suffered a COVID-19 infection at this time), they will be asked will to provide an equivalent sample at any time between November-December 2023 and their clinical record will be reviewed as above.

Visit 4: All participants will provide a sample 24-36 weeks post vaccination.

Visit 4 timelines are flexible and will depend on optimal time according to the planned vaccine schedule. The timing will be at least 24 weeks after the last vaccine but before the next planned vaccine.

Participants will be asked to complete the same electronic REDCap questionnaire as per visit 2.

Participants will be asked to provide the same samples as per visit 2 depending on whether they are the remote or in-person group.

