9.1 Anti-spike antibody testing

Antibodies will be tested using the Roche spike IgG quantitative assay (Birmingham). The assay detects anti-spike antibodies against the original Wuhan strain and so is suitable for detecting vaccine responses in a quantitative way. It will also detect antibodies following infection and cannot distinguish between these. It will be the primary platform to be used for all participants as it is already in widespread use by PHE and in the NHS. The Roche assay has been validated in Birmingham for DBS and shows excellent correlation and concordance with serum in providing a quantitative result. This remote sampling has been widely used for COVAD and other COVID-19 studies (PANORAMIC, COVIDENCE). To ensure applicability, the Roche assay performance will be compared with other platforms in use in the NHS using World Health Organisation (WHO) reference serum. This assay can be used to assess blood and mucosal samples.

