23.0 Appendix 3 Statistical analysis plan

Sample size and randomisation

We have assumed that a sample size of 3000 is feasible and that this is likely to be distributed as 750 in the "low response/no response" group and 2250 in the "normal response" group. We might then wish to estimate what difference between these two groups we could detect with 90% power. We have good estimates from previous studies over time in vulnerable populations and have therefore considered a range of infection and hospitalisation rates that might be plausible for this group. We have also considered the statistically most conservative option by setting the proportion at 50%.

In all cases, we can detect an absolute difference between groups of less than 10% and often less than 5% even for the rarer outcome of hospitalisation. These are consistent with a standardised effect sizes ranging from 0.15 to 0.36 for infection, which are consistent with small to moderate effects. The effect size for hospitalisation is less certain and ranges from 0.24 consistent with a small effect through to 1.33, a very large effect.

We consider this reassuring as it indicates that for a wide range of scenarios, we should have adequate power in the whole cohort for our primary outcome of infection and we may have power to detect a moderate effect for the rarer secondary outcome of hospitalisation, depending on the prevailing population rates and the variant of interest.

We will monitor all the assumptions that underlie these calculations at least monthly and will discuss monthly at our Trial Meeting Groups, if there are any concerns about power for key analyses.

Randomisation procedure

This is an observational cohort and participants will not be randomised. The cohort may be used in future to recruit to randomised trials and the process for selection and randomisation would be described accordingly in the associated trial protocol.

Statistical analysis considerations

Definition of analysis populations

CV groups are defined below and are derived in part from the QCOVID4 risk groups.

The Healthy Control (HC) group represent a population sampled from the PITCH Study (Protective immunity from T-cells in healthcare workers).

Baseline characteristics

At baseline the following characteristics will be described for the study cohort:

- Demographics (Age, BMI, self-reported ethnicity, sex, Index of Multiple Deprivation)

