- · Occupation, nature of work and type of personal protective equipment used during that work
- Medical conditions (self- reported)
- latrogenic immunosuppression (or within 6 months of iatrogenic immunosuppression including chemotherapy)
- · Vaccination history including COVID-19, influenza, and any test vaccines given
- · Known prior infection

Behavioural variables

If the participant self-isolated as a result of an illness in a household contact, we will collect data on the nature of that illness (when was illness, symptoms, severity, duration) and how many other household contacts were unwell.

Serological response

Time points for serological measurements: Assessment at 4 timepoints (Visit 1: baseline visit, Visit 2: before next vaccine dose, visit 3: 4 weeks post vaccine dose and Visit 4: 24-36 weeks post vaccine).

ii) 'Low' antibody range: Antibody values which lie within the lower 10th percentile of range of IgG antibody concentrations in HC following vaccine dose.

General analysis principles

- Summary statistics will include either mean, standard deviation, and/or median, interquartile range for continuous variables as appropriate to the distribution and n (%) for frequencies.
- The amount of missing data will be reported. Analysis will be of complete data and missing data will not be imputed.
- 5% two-sided level of statistical significance, with corresponding 95% confidence intervals presented where applicable.
- No adjustments for multiplicity are planned.

Planned analyses and reporting:

Primary Outcome

To assess the additive value of serological responses to CV status in predicting infection

The binary infection outcome will be captured by recording the timing and incidence rates of all infections from ≥14 days post vaccination given between Visit 2 until Visit 4 will be reported in the total combined CV groups, and by individual CV groups. We will describe the number and proportion of infections for each level of antibody response post-V3 (no, low, normal)

The primary analysis will be undertaken using a logistic regression model with infection as the outcome and antibody response post-V3 as a binary variable as the exposure. We will present odds ratios with 95% confidence intervals for the unadjusted model, as well as for a model adjusted for the baseline and behavioural variables as well as any COVID-19 therapy received in the community, preadmission and in hospital (where data available).

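### Prior infection is adjusted for only as known at Visit 1, so for people recruited before their booster an infection up to day 14 after the dose is neither covariate nor outcome in the primary analysis

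*Protocol*

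**What the plan says.** Section 11.0 names Appendix 3 as the statistical analysis plan, so the rule below is the stated one.

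- **Covariate.** Under Baseline characteristics, the list opens "At baseline the following characteristics will be described for the study cohort" and includes "Known prior infection". Appendix 3 identifies baseline with Visit 1.
- **Adjustment.** Odds ratios are given unadjusted and "for a model adjusted for the baseline and behavioural variables as well as any COVID-19 therapy received in the community". No infection after baseline is in that set.
- **Exposure.** The primary model takes "antibody response post-V3 as a binary variable as the exposure". Section 6.5.1 puts the Visit 3 sample 4 to 10 weeks after the dose.
- **Outcome.** It counts "all infections from ≥14 days post vaccination given between Visit 2 until Visit 4".
- **Reuse.** The time-to-event analysis takes the same covariates, and the severe-outcome analysis takes the same modelling approach.
- **Assay.** Of the primary anti-spike assay, section 9.1 says: "It will also detect antibodies following infection and cannot distinguish between these".
- **Data.** From Visit 2 on, the questionnaire asks for "Confirmation of any change in medical and drug history, COVID-19 infection and vaccination history" (section 6.5.1). Section 6.7 lets participants report an infection at any time.

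**The concern.** The covariate closes at Visit 1 and the outcome opens at day 14 after the dose. Visit 1 is a flexible time point. The 12-week rule for omitting Visit 2 shows that the protocol expects some participants to wait 12 weeks or more between Visit 1 and the booster. An infection in that interval can move a participant into the normal antibody group at Visit 3. If it also protects for some months, it is a common cause of normal antibody and of fewer later infections, and the adjusted model does not hold it.

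Two planned results are exposed:

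- the adjusted odds ratio for no/low antibody, in the primary, time-to-event and severe-outcome models;
- the added-value comparison, where serology may gain credit for recent infection history that the model without serology could have held.

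**Working it through.** **1. The plan's own figure.** Appendix 3 assumes 750 no/low and 2250 normal responders, 90% power and a two-sided 5% level. Solving the two-proportion power formula for the detectable difference gives:

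- at 50% in the normal group, 6.8 points (56.8% v 50%), odds ratio 1.32, standardised effect ln(1.315) × √3/π = 0.15;
- at 20%, 5.7 points (25.7% v 20%), odds ratio 1.38;
- at 3%, 2.7 points, standardised effect 0.37.

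This agrees with the plan's statement of less than 10% and with its range of 0.15 to 0.36. The plan does not print its base rates. Odds ratios of 1.32 to 1.38 serve as a yardstick below.

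**2. Inputs for the bias.** The 25% no/low share is the plan's (750/3000). The rest are assumptions:

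- the true antibody odds ratio is 1.00;
- later infection risk is 20% without a gap infection;
- 10% of gap-infected people are no/low at Visit 3;
- a gap infection multiplies the odds of later infection by ψ = 0.4 or 0.25;
- a share g of the whole cohort is infected in the gap.

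**3. Formulas, with g = 10% and ψ = 0.4.**

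- Later risk after a gap infection: odds 0.25 × 0.4 = 0.10, risk 0.10/1.10 = 0.0909.
- Gap-infected share of the no/low group: 0.10 × 0.10/0.25 = 0.04.
- Gap-infected share of the normal group: 0.10 × 0.90/0.75 = 0.12.
- Risk, no/low: 0.04 × 0.0909 + 0.96 × 0.20 = 0.1956.
- Risk, normal: 0.12 × 0.0909 + 0.88 × 0.20 = 0.1869.
- Odds ratio: (0.1956/0.8044)/(0.1869/0.8131) = 1.06.

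**4. Odds ratio read when the truth is 1.00.**

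| Infected in gap (whole cohort) | ψ = 0.4 | ψ = 0.25 |
|---|---|---|
| 5% | 1.03 | 1.04 |
| 10% | 1.06 | 1.08 |
| 20% | 1.12 | 1.17 |

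If 15% rather than 10% of the gap-infected are no/low, the range over the same grid is 1.02 to 1.11. With ψ = 1 every entry is 1.00.

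**5. Harsher assumptions.** These take 75% normal without a gap infection and 85% to 95% with one, and a relative risk of later infection of 0.2 to 0.8. At 10% gap infections the null odds ratio is then 1.01 to 1.11 (20% later risk) or 1.02 to 1.15 (40% later risk). At the top of those ranges, the chance of a significant excess in the no/low group rises from a nominal 2.5% to 17% and 34%. At 2% gap infections the odds ratio is at most 1.03.

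**6. How many gap infections are plausible.** Day 14 to Visit 4 at 24 to 36 weeks is 22 to 34 weeks. Suppose a 20% risk over that window at a constant rate. A participant with 12 weeks from Visit 1 to the dose has a 14-week gap, and a gap risk between 1 − 0.80^(14/34) = 9% and 1 − 0.80^(14/22) = 13%. If half the cohort had such a gap (an assumption) and the rest none, g would be about 4% to 7%. The 20% row is hard to reach.

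**The case against.** The strongest reply is that the objective is prediction. For that question, antibody raised by infection is part of the marker, and section 9.1 openly accepts that the assay mixes the two sources. This stands. A reader might infer that the whole excess in the table is bias, or that an observed antibody association would be spurious. The documents do not support that, because for prediction from antibody alone the excess is legitimate signal. What remains is the reading of the adjusted odds ratio and the fairness of the no-serology comparator.

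Other replies also hold in part:

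- **Not lost everywhere.** A reader might take these infections to be unused altogether. The secondary Visit 1 analysis describes infections up to Visit 2. That does not alter the primary model, and it has no natural end where Visit 2 is omitted.
- **Limited group.** Under Appendix 6, people recruited after the autumn 2023 booster give their first sample at least 28 days after the dose, as Visit 1, so their baseline history covers the period. Section 6.5.1 also foresees that some people infected around booster time will not be vaccinated. They have no index dose, so some gap infections never meet a window counted from vaccination.
- **Direction.** That a gap infection lowers later risk is not in the documents. It could instead mark higher exposure, which would pull the other way. The plan's choice to adjust for prior infection is consistent with protection but does not prove it.
- **Response model.** It might be said that the Visit 3 response model credits infection-derived antibody to the vaccine. That model estimates no vaccine effect and already allows further variables, so the point there is consistency only.

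Two possible safeguards do not close the gap. Adjustment for COVID-19 therapy would capture only treated infections. Nucleocapsid testing is an optional exploratory assay in section 9.2 and enters no model.

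**Conclusion.** The concern holds for the primary analysis and the models that reuse its covariates, and only for participants recruited before their booster. As written, the prior-infection covariate stops at Visit 1 although the exposure and outcome are timed from the dose. The likely distortion is small: a null odds ratio of about 1.03 to 1.04 at 5% gap infections and 1.06 to 1.08 at 10%, against a detectable odds ratio of 1.32 to 1.38. Apart from the 25% no/low share, every input is assumed, including the protective direction. The figures do not show that the primary result would be invalid. They show an avoidable weakness in an adjustment that the plan itself chose to make. It is worth correcting because the correction uses data already in hand.

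**What to change.** In Appendix 3, define known prior infection as any recorded infection before day 14 after the index dose, taken from the Visit 1 to 3 questionnaires, any-time reports and linked records. Use it in the adjusted primary, time-to-event, severe-outcome and added-value models, including the model without serology. Use the same variable in the Visit 3 response model. The day-14 limit keeps any one infection from being both covariate and outcome.

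A yes/no item does not change for someone already infected before Visit 1, so time since last infection may be added. Its form is for the trial statistician to choose, and the documents give no basis for a particular cut-off.

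Cost: a wording change, one derived variable and at most one or two extra parameters. No visit, sample or questionnaire item is added.

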5.0 Study population and eligibility criteria

5.1 Patient selection

Participants in this study will have an underlying disorder which has identified them as being clinically vulnerable. The disease and treatment groups eligible for participation (**TABLE 2, page 13**) in STRAVINSKY may alter throughout the study depending on the results from the retrospective analysis or other new knowledge/discussions such as the report from the Independent Advisory Group for COVID-19 medicines.⁵

TABLE 2. Groups eligible for participation

Group	Disease related groups (n=120-140 per group)				
1	Chronic lymphoproliferative disorders (footnote 1)				
2	Plasma cell disorders (footnote 2)				
3	Myelodysplastic syndrome (MDS) or (myeloproliferative neoplasms MPN) (footnote 3)				
4	Sickle cell disease, thalassaemia, or rare inherited anaemias				
5	Active malignancy diagnosed within 2 years of study consent (excluding non-melanoma skin cancer, non-invasive bladder cancer and localized squamous cell carcinoma of cervix)				
	(Note: participants who have received radiotherapy or systemic anti-cancer treatment within the last 26 weeks should be included in groups 18 and 19 first).				
6	Down's syndrome and learning disability				
7	Neurological diseases (Parkinson's and mult	iple sclerosis) (footnote 4)			
8	HIV				
9	Common variable immunodeficiency an prophylactic antibiotics and/or immunoglob	d secondary immunodeficiency (requiring ulin)			
10	Cirrhosis (footnote 5)				
11	Chronic respiratory conditions (footnote 6)				
12	Chronic kidney disease (CKD) stage 4-5 (foot	note 7)			
13	Diabetes mellitus (Type 1 and 2)				
14	Cardiac failure				
	Treatment-related group	Timing			
	(n=120-140 per group)				
15	Previous recipients of a solid organ transplant (SOT)	At any time			
16	Recipient of a haematopoietic stem cell transplant (HSCT)	Within 52 weeks at time of study consent			
17	Recipient of B-cell depleting treatment (APPENDIX 1 for details)	Within 52 weeks at time of study consent			
18	Recipient of systemic anti-cancer therapy e.g. chemotherapy or immunotherapy and others (APPENDIX 1 for details)	Ongoing or within last 26 weeks at time of study consent			
19	Recipient of radiotherapy	Ongoing or within last 26 weeks at time of study consent			
20	Autoimmune disease on systemic immunosuppressive* medication (APPENDIX 1 for details)	Ongoing or within last 26 weeks at time of study consent			

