6.0 Prospective study

6.1 Study design and overview

This is a multicentre prospective, observational cohort study (**FIGURE 1**). Patients will provide samples and clinical data on 4 different occasions over 12-18 months. For each of the 4 visits individuals will be allocated to be involved in the study either remotely or attend in-person.

3000 individuals will be recruited in total; for 2600 of these patients (remote cohort), their commitment to the study will be entirely remote.

400 individuals (in-person cohort) will be invited to attend a sampling appointment at one of the 4 inperson sampling sites (Birmingham, Southampton, Imperial or Oxford), for each of the 4 study visits. The aim will be to recruit between 120 and 140 individuals per disease/treatment group as detailed in **TABLE 2.**

13 | Page STRAVINSKY Protocol

^{*} This enables assessment of the primary outcome and response to bivalent vaccine. It is highly likely that policy on these licensed treatments will change, in which case we may submit an amendment to individuals receiving SARS-CoV-2 monoclonal Abs.

Informed consent and data collection will predominantly be collected online via a REDCap database. Patients and sites without access to devices or internet will be consented via telephone, the signed paper consent form will then be sent to the participant to counter sign, and they will be asked to post this back to the central study team.

Participants without access to devices to internet will also be offered face to face appointments where the patient can either be supported by the research nurse to complete the online consent form or the participant can sign a paper consent form. If paper consent forms are used, they will be transcribed/scanned into REDCap and the original paper source document will be stored at the recruiting site for the duration of the study. Any case report form (CRF) data collected face to face or via telephone will also be transcribed directly into the database by each local clinical care team. Paper CRF data and consent forms will be transcribed/scanned into REDCap. The original paper documents will be stored at the recruiting site.

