Assuming serology is predictive of outcome, we will build a model to explore the predictive value of key patient data and the added value of serological results. We will explore the discrimination and calibration of a model only including baseline and behavioural variables compared to this model also including serological response. Discrimination will be determined by Harrell's C statistic and calibration will be determined by the predicted probabilities for infection. It is not possible to externally validate this model in this study; instead 1000 bootstrapped samples will be used in determining the 95% confidence intervals for the C statistic.

As a sensitivity analysis we will also consider serological response as a continuous variable. We will also consider time to first infection as a time to event outcome with death as a competing risk. This will be implemented in Stata using the *stcrreg* command. The same covariates will be included in the adjusted model as for the primary analysis. Unadjusted and adjusted analyses will present hazard ratios with 95% confidence intervals.

To assess the additive value of serological responses to CV status in predicting severe outcome We will undertake an analysis using the same modelling approach as for the primary outcome but with a composite outcome of severe infection (infection, hospitalisation or death).

Secondary Outcomes

To evaluate the serological vaccine responses of CV patients to new vaccines

28-day post vaccine (Visit 3) IgG antibody levels (BAU/ml) will be reported in HC and CV individuals. The proportion of combined and individual CV groups with no, low or normal Visit 3 antibody levels will be reported.

The median (IQR) of Visit 3 antibody levels in each CV group will be reported, alongside the values for HC.

Logistic regression models will be used to assess factors that contribute to serological response as a binary outcome with normal compared to lack of response (no/low). The model will include the baseline variables set out in **Section 5.2** and further variables may be added to the model if evidence emerges that such variable impacts on vaccine responses to vaccines. Univariable logistic regression will be used to explore the unadjusted relationship of each variable with the outcome and multivariable logistic regression will be used to explore the independent relationship of each variable with the outcome. We will report odds ratios and 95% confidence intervals for all models.

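### The allocated CV group is missing from the adjusted primary model and from the added-value base model, although the stated aim is the value of serology added to CV status

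*Protocol*

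**What the plan says.** Appendix 3 of the protocol, under Primary Outcome, states the aim: "To assess the additive value of serological responses to CV status in predicting infection". A parallel aim, also framed as added to CV status, follows for severe outcome.

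Three models then serve the primary aim:

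- an unadjusted logistic model with "antibody response post-V3 as a binary variable as the exposure";
- "a model adjusted for the baseline and behavioural variables as well as any COVID-19 therapy received in the community", with therapy before and during admission also included where available;
- a comparison of discrimination and calibration for "a model only including baseline and behavioural variables compared to this model also including serological response".

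The baseline list in Appendix 3 covers demographics, occupation, self-reported medical conditions, iatrogenic immunosuppression, vaccination history and known prior infection. The immunosuppression item is extended by "or within 6 months of iatrogenic immunosuppression including chemotherapy". The Table 2 group is not on the list.

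Section 6.1 makes that group the recruitment unit: "The aim will be to recruit between 120 and 140 individuals per disease/treatment group". Below Table 2, section 5.1 assigns each participant one group by a hierarchy, with treatment groups first.

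**The concern.** A claim of value added to CV status needs a reference model that contains CV status. If the group is represented only partly, low antibody response can act as a marker of the group and take credit for what the diagnosis or treatment already tells the clinician. The reverse is also possible: if groups with many low responders have fewer infections for other reasons, a real association inside groups can be hidden.

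Quota recruitment sharpens this. The mix of groups is set by the design, so a pooled odds ratio without group terms depends partly on the quotas. What is at stake is whether the study can separate the information in an antibody test from the information in the patient's group.

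**Working it through.** **1. The plan's own figure.** Appendix 3 assumes 750 low or no responders and 2250 normal responders, 90% power and two-sided 5%. Taking 50% infection in one group, the detectable difference is 6.8 points (56.8% against 50%). The odds ratio is (0.5681/0.4319)/(0.50/0.50) = 1.32. The standardised effect is ln(OR) × √3/π = 0.15, which matches the lowest value stated for infection. The figure describes a crude two-group comparison and does not bear on whether group is in the model.

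**2. Overlap between the covariates and the group.**

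| Table 2 | Basis of allocation | Nearest covariate in Appendix 3 |
|---|---|---|
| Groups 1–14 | Main disease, if no treatment group applies | Self-reported medical conditions |
| Group 15 (solid organ transplant) | At any time | Immunosuppression current or within 6 months |
| Groups 16–17 (HSCT, B-cell depletion) | "Within 52 weeks at time of study consent" | The same item |
| Groups 18–20 | Ongoing or within 26 weeks | The same item; no separate radiotherapy item (group 19) |

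The overlap is real but incomplete. A participant in group 16 or 17 who is 27–52 weeks past treatment and has no other immunosuppression could be coded as unexposed. If the item is a yes/no flag, it would also merge different treatment groups.

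**3. Crude model, within-group OR 1.5 (assumed rates).** Take two strata of 1500 with low response in 45% and 5%. Low responders: 675 + 75 = 750. Normal responders: 825 + 1425 = 2250, which is the protocol's split.

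- Infection in normal responders 15% and 25%. An OR of 1.5 gives 20.9% and 33.3% in low responders. Pooled low: (675 × 0.2093 + 75 × 0.3333)/750 = 22.2%. Pooled normal: (825 × 0.15 + 1425 × 0.25)/2250 = 21.3%. Crude OR = **1.05**.
- Rates exchanged. Pooled low: (675 × 0.3333 + 75 × 0.2093)/750 = 32.1%. Pooled normal: (825 × 0.25 + 1425 × 0.15)/2250 = 18.7%. Crude OR = **2.06**.

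This is not mere non-collapsibility of the odds ratio. With 25% low responders in both strata, the pooled rates are (0.2093 + 0.3333)/2 = 27.1% and (0.15 + 0.25)/2 = 20%, and the crude OR is 1.49.

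**4. Crude model, no within-group effect (assumed rates).** With low response 40% and 10% and infection 30% and 20%, pooled rates are (600 × 0.30 + 150 × 0.20)/750 = 28% and (900 × 0.30 + 1350 × 0.20)/2250 = 24%. The crude OR is 1.23, and the null is rejected 59% of the time. Twelve such scenarios were tried: low-response shares from 30/20 to 45/5, crossed with infection 25/20, 30/20, 40/20 and 15/25. The crude OR ran from 0.70 to 1.63.

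**5. Twenty groups of 150, no within-group effect (simulation, 200 runs per scenario).** Group log-odds of low response had SD 1.2. Group log-odds of infection had SD 0.2 or 0.4. Their correlation was 0, 0.5 or 0.8.

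| Model | Mean OR | Rejection at 5% |
|---|---|---|
| Antibody only | 0.99 to 1.30 | 7.5% to 75% |
| Antibody + 20 group indicators | 0.99 to 1.01 | 4% to 6.5% |

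**6. A partial proxy (assumed rates).** Suppose a yes/no immunosuppression flag is the only adjustment, and flag-positive participants form two equal halves with low response 60% and 20% and no within-half effect.

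- Infection 25% and 15%: low (0.60 × 0.25 + 0.20 × 0.15)/0.80 = 22.5%; normal (0.40 × 0.25 + 0.80 × 0.15)/1.20 = 18.3%; OR 1.29.
- Infection 15% and 25%: 17.5% against 21.7%; OR 0.77.

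Self-reported conditions would reduce this distortion by an amount that cannot be computed from the protocol.

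**The case against.** The strongest reply is that CV status is already in the models under another name. CV groups are defined by conditions and treatments, and both are among the baseline variables. Section 6.4 has participants state at enrolment which Table 2 groups they belong to, and section 6.5.1 adds conditions and medication from records. Separately coded conditions might even carry more than a single group assigned by hierarchy. This stands in part. A reader might infer that the adjusted and base models hold no CV information; the documents do not support that.

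A reader might also infer that every HSCT or B-cell-depletion participant treated 27–52 weeks earlier is coded as unexposed. That goes too far: current immunosuppression counts whenever the index treatment was given.

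The odds ratios of 1.05 and 2.06 belong to the crude model, which the plan openly labels unadjusted and presents beside the adjusted one. They do not measure bias in the adjusted model or in the C statistic.

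The plan also reports infections by CV group and fits the primary model within groups if numbers allow. Those fits do remove between-group mixing, but they are exploratory and conditional and give no pooled within-group estimate.

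Finally, variable coding may sit in a fuller analysis plan that is not shown. That would answer a complaint about coding. The point here is that Appendix 3 fixes the covariate set and the allocated group is not in it.

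**Conclusion.** The point holds in a limited form. The aim names CV status as the comparator, while the allocated group that defines it for recruitment is absent from the adjusted primary model and from the base model of the added-value comparison.

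For the crude odds ratio the mixing can be large: 1.05 to 2.06 for a within-group value of 1.5, and 0.70 to 1.63 for a within-group value of 1. Every group rate behind these figures is assumed. Section 2.0 says that vaccine response is heterogeneous in disease populations, but no response or infection rate by group is given.

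For the adjusted and prediction models the mixing is residual, and its size cannot be determined from the protocol. It could be small if conditions and treatments are coded close to the Table 2 categories. It would be wrong to conclude that the study cannot answer its question; as written, the plan does not ensure that it will.

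**What to change.** Add the allocated Table 2 group (20 levels), as fixed effects or a random intercept, to the adjusted primary model and to both the base and the serology-added prediction models. Carry the same change into the severe-outcome analysis, which uses the same approach. State that the added-value conclusion rests on these models and that the crude odds ratio is descriptive.

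Fixed effects are the more direct choice, because a random intercept shrinks the group effects and can leave some of the mixing. Keep the condition and treatment covariates, since one group assigned by hierarchy does not capture multiple conditions, and state how they are coded.

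The cost is a wording change and no new data, because section 5.1 already assigns the group. Statistically it uses up to 19 degrees of freedom, or one variance term, and brings some collinearity with the condition and treatment covariates. Replacing the exploratory subgroup fits by a group-specific antibody slope is optional and not needed for this point.
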